CHOP is a prospective observational cohort study with four tracks ([1] medical professionals, [2] community, [3] employee, and [4] randomized controlled trial [RCT]) to allow results to be compared among the subjects in the four tracks. [1] Current and future medical professionals will be trained in classes within their track in how to educate patients about nutrition, and their results for their DACs will be compared to those who receive traditional clinical education. [2] Adults, adolescents, and children 7 years and older will be offered classes in their community track to allow comparison of their DACs and health metrics with those who do not take the classes. [3] Employees and their families who take the GCCM classes as employee wellness programing will have their DAC and health metrics compared to employees who do not take the classes. And finally, [4] subjects with such chronic health conditions as diabetes will be randomized with equal 50% chance to either taking the GCCM classes or receiving medical nutrition therapy (MNT) with a registered dietician (RD).

DAC surveys will take place for the first track at the beginning and end of each academic year. Surveys will take place for the last three tracks at the first and last class for the treatment (GCCM) class group, and the beginning of the study and 2-3 months later for the control groups (those who do not take the classes). The same adult and children surveys will be used across tracks [2]-[4] for adults 18 years and older and children 7-17 respectively. Medical professionals in [1] will have the same survey.

CHOP unites such analyses as diffusion of innovation (DOI), social network, and simulation-based medical education with deliberate practice (SBME-DP) along with rigorous statistical methods to answer these questions and hopefully benefit society. Results will be strengthened by using self regulation survey with Tulane marketing students to better design the DAC survey based on understanding what DACs predict

Version Date: 09/26/15 Version Number: 1 Page 2 of 9 certain nutrition behavior, in addition to comparison to the de-identified National Health and Nutrition Examination Survey (NHANES) for national trends in diet and similar health metrics and behaviors.

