# 3. Procedure

[1] Medical professionals track: An internet link will be distributed to subjects through the list-serves for each class at the beginning and end of each academic year after they have had the opportunity to participate or not in the voluntary GCCM classes. Residents and practicing physicians who identify themselves through the GCCM website will be subsequently offered the survey. Marketing students will be offered an online survey about self-regulation and nutrition through their marketing class to improve the medical professionals survey.

[2] Community, [3] Employee, and [4] RCT tracks: Subjects in the treatment group will receive up to 20 evidence-based classes (50 hours) of cooking and nutrition education that cover the Mediterranean diet, food shopping, cooking, and storage. Subjects in the control groups for [2] and [3] will not receive the classes, and control subjects in [4] will receive MNT. Control subjects in [2] will additionally have the opportunity to receive either healthy food vouchers for 2 months or have nutrition education for their children before they enroll in the classes in order to compare if increased healthy food access and education compared to GCCM classes best prepares them to benefit from nutrition education. DAC surveys will be used at the beginning and end of the classes for the treatment group, and beginning of the study and 2-3 months later for the control group. Health metrics will be assessed from health records for subjects retrospectively 3 years before and 3 years after their treatment or control exposure, once subjects provide release to the study team of their records with appropriate safeguards to protect

Version Date: 09/26/15 Version Number: 1 Page 3 of 9 the safety of their data. Recruitment for [2] will be through GCCM's website, [3] will be through Laitram that promotes the classes to their employees, and [4] through Tulane University Hospital and Clinic (including the Internal Medicine Practice, Uptown Square clinic, Endocrinology clinic, and Metairie Multispecialty clinic) by study staff. Health metrics will be obtained for [2,4] from Tulane University Hospital and Clinic if subjects' information is stored there, from Marathon Health the third party provider of health care for [3], and from non-Tulane health care institutions for [2,4]. Marathon and non-Tulane facility health information release forms will be provided to subjects as needed at the time of informed consent.

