#### 10. Consent process and documentation

[1] Medical professionals track: A waiver of documentation of consent has been attached to this package for both medical professionals and trainees and marketing students, due to the information necessary for informed consent being provided in the recruitment email and the significant logistical challenges of documenting consent individually for such a large number of respondents remotely accessing the survey through the confidential online survey link. Email addresses are collected to verify the accuracy of the self-generated dummy IDs for subjects who respond to repeat surveys, and then the emails are deleted from the dataset used for longitudinal analysis.

[2] Community, [3] Employee, and [4] RCT tracks: A full description of the research will be discussed with subjects regarding both study groups. Discussion about the risks and benefits will be undertaken with prospective participants. This will mirror the written information in the consent form. After full information is discussed and questions are answered the participants the consent form will be reviewed and subjects will be asked to sign the form if they are interested in being involved (adults) or assent (children). Telephone numbers are collected based on GCCM experience over the past four years that class participants find reminders about classes helpful.

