# 12. Survey links

[1] CHOP-Medical Professionals: http://tulane.qualtrics.com/SE/?SID=SV\_57Pu9twXUczA4gR.
[2-4] CHOP-Community, -Employees, -RCT Adults: http://tulane.qualtrics.com/SE/?SID=SV\_5C5tqoWuaGK4esR.
[2-4] CHOP-Community, -Employees Children: http://tulane.qualtrics.com/SE/?SID=SV\_08RuXreVqaFzV0F.
[Supplemental] Self-regulation: http://tulane.qualtrics.com/SE/?SID=SV\_beARYSuPFbCp9pH.

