# **Statistical Analysis Plan**

# **Power Analysis**

The required calculated sample size to achieve 80% power and detect an odds ratio (OR) of at least 1.50 with a two-sided test set at 5% was 263 cases.

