Doubly robust estimation features a dual strategy of outcome regression that also accounts for the likelihood of receiving an exposure or treatment, such as with a PS. Simply using multivariable regression or PS analysis can lead to biased treatment estimates if either model is incorrectly specified. But with doubly robust estimation using both concurrently, only one model must be correctly specified to produce unbiased estimates. Of all the forms of PS analysis (i.e., matching, stratification, weighting, and adjustment), regression that includes the PS as one of the adjusted variables has quantitative evidence as being the top performing PS method. Finally, mixed effects regression further provides a powerful approach to causal inference. This mixed method contains both fixed effects (FE) and random effects (RE) components, with FE having the distinct advantage of controlling even for nonobserved traits by controlling for all time-invariant traits. FE does this by setting each individual subject as his/her own control and thus models within-person effects. Aside from the theoretical advantages, FE has shown quantitative strengths over competing methods. RE was used to control for what FE cannot,

Version Date: 09/26/15 Version Number: 1 Page 8 of 9 namely, time-varying traits at the individual level with repeated observations over time (as students progressed through their medical education). The multilevel aspect was used to account for the hierarchical nature of the data in which medical trainees responded from different medical institutions. Inverse-variance weighted fixed effects (IVWFE) meta-analysis was used to produce a composite estimate across the 25 competency topics.

This triply robust approach can be represented by the following mathematical formula:

$$\Pr(y_{ij} = 1 \mid u_j) = H(x_{ij}\beta + z_{ij}u_j)$$
(1)

for *M* independent clusters conditioned on random effects  $u_j$  for j = 1, ..., M clusters with cluster *j* constituting  $i = 1, ..., n_j$  observations, outcome  $y_{ij}$ , FE covariate  $x_{ij}$ , RE covariate  $z_{ij}$ , and regression coefficient  $\beta$ , all within a logistic regression equation with logistic cumulative distribution function of  $H(\bullet)$ . The PS is utilized as an additional variable in the above model and is represented as

$$e(x_i) = \Pr(z_i = 1 \mid x_i)$$
(2)

in which exposure probability is conditioned on the covariate  $x_i$  observed.

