The competing causal inference methods of instrumental variable and difference in difference analyses were not utilized due to their methodological weaknesses, respectively, of having varying degrees of reliable instrumental variables and having a prevalence of unobserved confounders exerting time-varying effects before and after the exposure/treatment. The above methods of doubly robust PS adjustment in multivariable regression were therefore integrated with multilevel mixed effects to provide a novel triply robust approach to causal inference. Aside from controlling for the likelihood of receiving GCCM education (via the PS) and unobserved time-invariant traits (via FE) and time variant along with intracluster correlation (via RE), this integrative method controlled via regression for age, gender, race, prior nutrition education, special diet, school year, intended specialty, and medical school. This multilevel approach has a Bernoulli conditional distribution of the response given the random effects and logistic cumulative distribution function for the success probability.

All results are reported as fully adjusted ORs. ORs rather than relative risks were calculated due to the complex data source described above and due to the rare disease assumption. Statistical significance was set at a two-tailed *p* value < 0.05. ML analysis was performed in R 3.3.2 (The R Foundation for Statistical Computing, Vienna, Austria). Statistical analysis was performed in STATA 14.2 (STATACorp, College Station, Texas, United States of America). Ethics approval was obtained through the Institutional Review Board (IRB) of Tulane University.

Version Date: 09/26/15 Version Number: 1 Page 9 of 9

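### The composite odds ratio pools 25 topic estimates as if independent; if they are positively correlated, its standard error is too small and its test exceeds 5%

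*Combined protocol and SAP*

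**What the plan says.** The SAP gives the composite one sentence, under Machine Learning and Statistical Analysis: "Inverse-variance weighted fixed effects (IVWFE) meta-analysis was used to produce a composite estimate across the 25 competency topics". It prints no variance formula. Results are adjusted odds ratios judged at a two-sided 5% level.

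Three places in the protocol bear on where the 25 estimates come from:

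- Section 1, on track 1: "Medical professionals in [1] will have the same survey".
- Section 3, on track 1: "An internet link will be distributed to subjects through the list-serves for each class at the beginning and end of each academic year".
- Section 12 lists a single survey for medical professionals.

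The SAP describes its handling of correlation only inside a regression model. Random effects are for repeated observations over time, and the multilevel term is for institution. Equation (1) has an observation index and a cluster index, and no topic index. The fixed-effects component is described as "setting each individual subject as his/her own control and thus models within-person effects".

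**The concern.** Inverse-variance fixed-effects pooling was built for separate studies with different participants. Here the 25 inputs seem to be 25 outcomes measured on the same people. A trainee who rates one competency highly probably rates others highly too, so the topic log odds ratios would tend to err in the same direction. Pooling them as independent then counts much of the same information up to 25 times.

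The composite is the only cross-topic summary of the competency results that the SAP states. If its standard error is understated, its p value is too small and any interval around it too narrow.

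**Working it through.** **Inputs.** Number of pooled estimates: 25 (SAP). Level: two-sided 5% (SAP). Correlation rho between topic log odds ratios after adjustment: not in the documents, so every value below is an assumption. Pooling on the log odds ratio scale is the usual reading and is not stated.

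**The plan's own figure.** The documents give no composite standard error to reproduce. The Power Analysis states a size: "with a two-sided test set at 5% was 263 cases". It gives no baseline rate, allocation or formula, so that number cannot be checked. Nothing in the closed form depends on it; the simulations borrow 263 as an assumed number of respondents.

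**Closed form.** With weights w = 1/SE²:

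- Variance used by standard pooling: 1/Σw.
- Actual variance: 1/Σw + Σ(i≠j) w_i w_j cov_ij / (Σw)².

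All weights are positive, so uniformly positive covariances make the first expression too small. For 25 equally precise estimates with common correlation rho, the ratio of actual to nominal SE is √(1 + 24·rho), and the actual type I error is 2·(1 − Φ(1.96/ratio)).

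| rho (assumed) | SE ratio | Type I error |
|---|---|---|
| 0 | 1.00 | 5% |
| 0.02 | √1.48 = 1.22 | 11% |
| 0.05 | √2.2 = 1.48 | 19% |
| 0.1 | √3.4 = 1.84 | 29% |
| 0.3 | √8.2 = 2.86 | 49% |

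The error reaches 10% when the ratio is 1.96/1.645 = 1.19, that is at rho = (1.19² − 1)/24 ≈ 0.0175.

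*Unequal precision.* Replace 24 by (Σ√w)²/Σw − 1. For topic SEs spread threefold on a geometric scale this is 21.59, and the errors at rho 0.02, 0.05, 0.1 and 0.3 become 10, 17, 27 and 47%.

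*Partial response.* If each topic is rated by a random fraction q of respondents, rho becomes q·rho. With q = 0.5, a rho of 0.1 falls to 0.05 and the error from 29% to 19%.

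*Illustration of width.* Suppose each topic has an odds ratio of 1.50 with SE = ln(1.50)/(1.96 + 0.84) = 0.145. The nominal pooled SE is 0.145/5 = 0.029, giving a 95% interval of 1.42 to 1.59. At rho 0.1 it should be 1.35 to 1.67, and at rho 0.3, 1.28 to 1.76.

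**Simulation under no effect.** How much correlation survives depends on the fitted model, so three simplified models were run: 25 binary topics, 263 respondents, 1,000 replicates per setting (Monte Carlo error about ±1.4 points at 5% and ±3.1 at 50%). Shared variation is given as an assumed SD in logits. Rejection rates for standard pooling at a nominal 5%:

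| Model | Assumed shared variation | Type I error |
|---|---|---|
| (a) One observation each; propensity score, 3 covariates, 4 institutions; no person term | Trait SD 0, 0.3, 0.5, 1.0, 1.5 | 5.6, 8.5, 20.0, 37.9, 49.1% |
| (b) Two waves, respondent random intercept | Trait SD 0, 0.4, 1.0 | 3.9, 13.5, 28.4% |
| (b) as above, trait SD 1.0 | Occasion SD 0.3, 0.5, 1.0 | 35.7, 37.9, 44.3% |
| (c) Two waves, strictly within-person | Trait SD 0, 0.4, 1.0; no occasion effect | 4.1, 3.0, 4.8% |
| (c) as above | Occasion SD 0.3, 0.5, 1.0 | 13.6, 16.7, 38.5% |

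Models (b) and (c) have half the respondents exposed at wave 2 and omit the propensity score, covariates and institution. In (a), trait SDs of 0.5, 1.0 and 1.5 correspond to rho of about 0.05, 0.17 and 0.29, for which the closed form gives 19, 38 and 49%, so the two approaches agree. At an assumed 627 respondents, (a) gave 5.9, 10.7, 18.5, 36.5 and 47.1%: a larger sample does not cure the problem. Further runs gave similar results, including about 4% for a strictly within-person fit, rising to 10–36% with occasion-level variation.

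**Remedy under the same simulations.** Keeping the point estimate and using a covariance clustered on respondent gave 3.5–6.2% in every setting.

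**The case against.** The strongest counter-argument is that, on the SAP's own prose, the effect may be nil. If each trainee is truly their own control, a stable tendency to rate highly drops out, and model (c) shows 3.0–4.8% without occasion-level variation. This is a fair limit on the size of the problem, but it does not remove it. Equation (1) is written as a random-effects logistic model, and the SAP adjusts for gender and race, which a strictly within-person fit would ordinarily drop. Even within person, a mood or response style shared across one sitting brings the inflation back.

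Other points that stand:

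- Rho is unknown, and that the same respondents rated all 25 topics is inferred. The survey itself is not shown.
- Section 2 of the protocol describes trainees at one university, while the SAP refers to several institutions, so the analysed data may not be exactly those described in Sections 1, 3 and 12.
- The SAP refers back to literature and a data source that are not in the text supplied. The absence of any handling of dependence is a statement about the documents as held.
- The SAP does not name a confidence interval. The same standard error, however, drives the p value it does use.
- The simulated models are simpler than the SAP's model, so their rates are not forecasts.
- The composite is not called primary.

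**Conclusion.** The concern holds in its conditional form. The stated method assumes independence by default, the random and multilevel terms do not supply covariance between separate topic estimates, and positive correlation makes the composite's standard error too small. Confidence in that statement is high. Confidence that the effect is material in this study is medium, because it rests on overlapping respondents and on an unreported correlation. The margin is thin: for 25 equally precise estimates, a correlation of only 0.0175 doubles the error to 10%.

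The problem is one of precision and type I error for a single summary in track 1. It should be fixed before the composite's p value, or any interval around it, is relied on.

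**What to change.** Keep the inverse-variance point estimate. Base its p value and any interval on the variance w'Vw/(Σw)², where V is the 25 × 25 joint covariance of the topic log odds ratios clustered on respondent. V can come from a joint robust covariance, or from a bootstrap that resamples whole respondents and respects institution. State in the SAP whether the fitted model is within-person or random-effects, and whether each respondent rated all 25 topics.

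This needs about one added SAP sentence, some code and computing time, and no new data. Section 10 of the protocol says email addresses are collected "to verify the accuracy of the self-generated dummy IDs for subjects who respond to repeat surveys", so respondent-level linkage should be available. Because the SAP is written in the past tense, the change probably means re-running the composite analysis, and a bootstrap over 25 multilevel fits is the heavier option. The remedy has been tested only in the simplified models above, so its behaviour in the full multilevel model should be checked. If the topics are positively correlated, the interval widens; if the correlation is negligible, the result should barely change.

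### The SAP's reason for excluding difference-in-differences applies equally to the regression it keeps, and the three pre-exposure record years in tracks 2 and 3 have no stated role

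*Combined protocol and SAP*

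**What the plan says.** The SAP (Machine Learning and Statistical Analysis) presents a panel regression for causal inference and explains why DiD was not used: it suffers from "having a prevalence of unobserved confounders exerting time-varying effects before and after the exposure/treatment".

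The same section describes how the retained model deals with confounding:

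- Fixed effects: "FE having the distinct advantage of controlling even for nonobserved traits by controlling for all time-invariant traits". The mechanism given is that "FE does this by setting each individual subject as his/her own control and thus models within-person effects".
- Random effects are said to control what fixed effects cannot, "namely, time-varying traits at the individual level with repeated observations over time (as students progressed through their medical education". The closing summary repeats the split: "unobserved time-invariant traits (via FE) and time variant along with intracluster correlation (via RE".
- The propensity score is a probability "in which exposure probability is conditioned on the covariate" observed (formula 2).
- Regression adjusts for eight listed covariates. None is a health metric or a pre-exposure value.

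Protocol section 3 (Procedure), for tracks 2 to 4, states: "Health metrics will be assessed from health records for subjects retrospectively 3 years before and 3 years after their treatment or control exposure". Section 1 compares those who take the classes with those who do not in tracks 2 and 3, without randomisation.

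**The concern.** A reason for rejecting one method should not equally disqualify the method chosen instead. Here it appears to, and the component credited with closing the gap, the random effect, cannot do so.

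The practical stake is in tracks 2 and 3. People decide whether to take the classes. If those who join have recently had a poor reading, or are already on a different course, their later values will differ from those of non-takers with no class effect at all. Three years of earlier records in both groups are the one planned source of information on this, and the SAP does not say how they will be used.

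**Working it through.** **1. Does the stated ground separate the two methods?** The plan has no figure of its own on this point (the 263 cases in the Power Analysis do not bear on it), so the components are set side by side.

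| Component | What it removes | Unobserved time-varying confounding |
|---|---|---|
| Fixed effects | Stable traits, by the SAP's own account | Remains |
| Propensity score (formula 2) | Observed covariates; no time index | Remains |
| Regression covariates | The eight listed items | Remains |
| Random effect u_j (formula 1) | Nothing; it models correlation within clusters | Remains |
| DiD | Stable group differences and shared time changes | Remains |

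Fitting formula (1) means averaging over a distribution of u_j that does not depend on the covariates, exposure included. A term assumed independent of exposure cannot absorb a confounder, which by definition is related to exposure. Formula (1) also shows no subject-specific fixed intercept, time term or pre-exposure trend term.

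**2. What happens under different kinds of confounding?** Illustration with assumed effect sizes and no class effect: 1,500 takers and 1,500 non-takers (track 3 targets), six yearly binary readings, 300 runs. Entries are the proportion with |z| > 1.96.

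| Scenario | Within-person FE | DiD, all years | Pre-exposure trend test |
|---|---|---|---|
| Stable level difference | 0.04 | 0.06 | 0.05 |
| Differing trend, 0.05 log-odds per year | 1.00 | 0.90 | 0.13 |
| Change of 0.3 log-odds at enrolment | 1.00 | 1.00 | 0.06 |
| Dip of 0.3 log-odds in last pre-exposure year | 0.53 | 0.33 | 0.74 |

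Both methods cope with stable differences and both fail otherwise. The pre-exposure years help only in part. The trend test usually flags a dip, seldom flags a slow trend, and cannot see a change that coincides with enrolment. Extrapolating a linear pre-exposure trend corrects the trend case (0.03) but makes the dip case worse (0.85).

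**3. Enrolment after a poor reading.** Assumed inputs: 3,000 subjects, three yearly blood-pressure readings before and three after, mean 135, between-person SD 12, within-person SD 8 mmHg, outcome below 140, no class effect. Enrolment odds rise 1.35-fold or 1.82-fold per SD of the last pre-enrolment reading.

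Size in mmHg if that last reading is the baseline:

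- Total SD = √(12² + 8²) = √208 = 14.42. Share that reverts = 64/208 = 0.308.
- Odds 1.35: ln 1.35 = 0.300; group gap ≈ 0.300 × 14.42 = 4.33; reversion ≈ 4.33 × 0.308 = 1.33 mmHg.
- Odds 1.82: ln 1.82 = 0.599; gap ≈ 8.64; reversion ≈ 2.66 by this linear approximation, 2.5 by simulation.

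Random-intercept logistic fits, 100 datasets per scenario (Monte Carlo standard error about 4 points at 20% and 5 points at 50%):

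| Analysis | Rejects at p < 0.05 (odds 1.35; 1.82) | OR (odds 1.35; 1.82) |
|---|---|---|
| Exposure term only | 20%; 50% | 0.94; 0.90 |
| DiD, all years | 18%; 55% | 1.09; 1.20 |
| DiD without last pre-enrolment year | 6%; 8% | 0.99; 1.00 |
| Pre-exposure contrast (year −1 against −3 and −2) | flags 60%; 100% | – |

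The exposure-only model errs towards apparent harm, because takers have higher pressure throughout and that difference enters the exposure term. All-years DiD errs towards apparent benefit. The direction of bias therefore depends on how the model is coded.

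**The case against.** **The SAP text is about track 1.** Its clusters are medical institutions, its covariates include school year and intended specialty, and its composite covers 25 competency topics. It never mentions health metrics or tracks 2 to 4. This stands. A reader might infer that rejecting DiD is why the pre-exposure years go unused. The documents do not support that: their use is unspecified, not excluded, and the cause is the missing analysis for these tracks.

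**The SAP has an answer: random effects handle time-varying traits.** It does say so, and that is how it separates its method from DiD. The answer fails for the reason in step 1, so the claim itself needs correcting.

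**DiD would do no better.** Correct for ordinary DiD, as both tables show. The gain comes from the pre-exposure contrast and from omitting the last pre-enrolment year. In step 3 that omission works partly by construction, because the simulated yearly errors are independent. It would not cure a differing trend.

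**The simulated comparator is not the SAP model.** True: the exposure-only fit has no propensity score, covariates or subject fixed effects. Its rejection rates do not estimate the SAP model's error rate.

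**Self-timed enrolment is an inference.** The protocol describes website recruitment, employer promotion, and some track 2 controls enrolling later. It does not say how start dates are set or what date stands for exposure in a control.

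**Conclusion.** The point holds in a limited form. The ground given for excluding DiD does not distinguish it from the retained regression, and the statement that random effects control time-varying traits is incorrect. On this point the causal-inference label has no support. This part is a matter of logic and needs no assumed numbers.

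For tracks 2 and 3, the finding is that health metrics have no specified analysis and the pre-exposure years no stated role. Carrying this model over with a causal label would leave differing pre-exposure courses undetected and uncorrected. The size is not known from the documents. The illustration gives 1.3 to 2.5 mmHg and false rejection of 18% to 55% for all-years DiD, resting wholly on assumed blood-pressure variation and strength of selection.

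Two stronger readings should be resisted. One is that adopting DiD would itself solve the problem; it would not. The other is that ruling out instrumental variables is an error because track 4 has subjects "randomized with equal 50% chance to either taking the GCCM classes" or dietitian-led therapy. Random assignment could serve as an instrument for an effect of attendance, but no document plans such an analysis.

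**What to change.** In the SAP:

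1. Delete the stated ground for excluding DiD and the claim that random effects control time-varying confounding.
2. For health metrics in tracks 2 and 3, define an index date for non-takers and state how controls who later enrol are handled.
3. Report the between-group difference in pre-exposure change (year −1 against years −3 and −2) with its confidence interval. A non-significant result should not be read as proof of comparability.
4. Estimate the group-by-period effect with the last pre-enrolment year omitted, at least as a sensitivity analysis.
5. If the groups differ before exposure, describe the result as an association. In every case, note that a change coinciding with enrolment cannot be detected.

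The cost is SAP wording and a few model terms, using records the protocol already plans to obtain. Omitting one of three pre-exposure years loses a little precision. The analysis also depends on records being available in each pre-exposure year, which the protocol does not promise.

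### The track 1 model has no start/end-of-year term, so if exposure is coded as changing between the two surveys, ordinary change over the year enters the class odds ratio

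*Combined protocol and SAP*

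**What the plan says.** **Survey timing.** Protocol section 1: "DAC surveys will take place for the first track at the beginning and end of each academic year". Protocol section 3 places the survey link "at the beginning and end of each academic year after they have had the opportunity to participate or not in the voluntary GCCM classes". The natural reading is that the classes fall between the two surveys of a year.

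**The claimed contrast.** The SAP (Machine Learning and Statistical Analysis) describes a panel analysis for causal inference. It credits fixed effects with "controlling even for nonobserved traits by controlling for all time-invariant traits" and adds: "FE does this by setting each individual subject as his/her own control and thus models within-person effects". Random effects are assigned to "time-varying traits at the individual level with repeated observations over time".

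**The model terms.** The same section says that "this integrative method controlled via regression for age, gender, race, prior nutrition education, special diet, school year, intended specialty, and medical school". Equation (1) is a mixed logistic model with generic covariates and no period effect written out. Equation (2), the propensity score, is one "in which exposure probability is conditioned on the covariate" vector, and it is indexed by subject only.

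**Difference-in-difference.** This is set aside for "having a prevalence of unobserved confounders exerting time-varying effects before and after the exposure/treatment".

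The SAP does not say how exposure is coded at each survey.

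**The concern.** Between the start and end of a year every trainee, class-taker or not, receives a year of clinical education and answers the same questionnaire again. Competency answers may shift for those reasons alone. A causal reading of the class OR requires that shared shift to be estimated and removed.

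Nothing in the stated model does this explicitly. School year cannot, because it does not change between the two surveys of one year. Random effects cannot, because they are deviations around zero and a shift common to all has no place in them. The propensity score concerns who takes classes, not when the survey was answered.

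The problem is separate from self-selection: it would arise even if takers and non-takers were identical at baseline. At stake is whether a significant class OR could appear when the classes do nothing.

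**Working it through.** **Inputs.** From the documents: two surveys per year with classes between them (protocol sections 1 and 3), the eight listed covariates and equations (1) and (2) (SAP), and a target OR of 1.50 (SAP, Power Analysis). Not given, so assumed: the size of the ordinary yearly change, the share taking classes, and the between-person spread. The SAP's 263 cases cannot be reproduced without an outcome prevalence and an exposure ratio, and nothing below depends on it.

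**Step 1: pure within-person contrast.** For person i at survey t, let w = 0 at the start and 1 at the end, and let e be exposure, coded as changing between surveys:

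logit P(y = 1) = a_i + γw + βe

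Among people whose answer changes, the odds of changing from 0 to 1 rather than from 1 to 0 are exp(γ + β) for takers and exp(γ) for non-takers. If w is omitted, a non-taker has no covariate that changes within the year and contributes nothing. The estimate is then the takers' own ratio n01/n10, so

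estimated class OR = yearly-gain OR × true class OR.

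For a gain OR of 1.5 and a true class OR of 1.0 this is 1.5 × 1.0 = 1.5, which equals the plan's target effect. If scores fall by the same factor it is 1/1.5 = 0.67. With w included, non-takers identify γ, and the class OR becomes the takers' ratio divided by the non-takers' ratio.

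**Step 2: mixed model, two surveys.** Simulated with a true class OR of 1.0, person SD 1.5 on the logit scale, baseline logit −0.6 and 30% or 50% taking classes. Rejection rates are for 1,000 people. Ranges cover repeated simulations.

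| Assumed yearly-gain OR | Proportion, start to end | Pure within-person OR (step 1) | Mixed-model OR, no start/end term | Runs with p < 0.05 |
|---|---|---|---|---|
| 1.25 | 40% to 43% | 1.25 | 1.14–1.18 | 12–23% |
| 1.5 | 40% to 47% | 1.50 | 1.30–1.37 | 38–61% |
| 2.0 | 40% to 52% | 2.00 | 1.59–1.71 | 82–98% |

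With a start/end term the mixed-model OR is 0.95–1.01, with 3–8% rejections.

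The mixed model carries only part of the gain because it also uses between-person information. Non-takers' end-of-year answers sit in the unexposed reference and pull it upward.

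**Step 3: does school year help in longer panels?** In part.
- Two years, four surveys, person SD 1, school-year term, gain not retained into the next year: the pure within-person OR is 1.20, 1.42 and 1.85 for gains of 1.2, 1.5 and 2.0. The random-intercept OR is 1.17, 1.20 and 1.44. Adding a start/end term to the within-person fit gives 1.03–1.05.
- Four years, ever-exposed coding, school-year factor: the mixed-model OR is about 1.05 for a gain of 1.2 and 1.20–1.24 for a gain of 1.5.

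**Step 4: the alternative coding.** With a fixed taker/non-taker indicator (person SD 1.5, 30% uptake per year, gains of 1.2–1.5, panels of one, two or four years), the OR is 0.92–1.02, the same with or without a start/end term.

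**Step 5: pooling.** The inverse-variance composite over 25 topics would not average out a shift in the same direction across topics. It would narrow the interval around it.

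**The case against.** The strongest reply is that the exposure coding is inferred. Equation (2) indexes exposure by subject, and the protocol speaks of comparing class-takers with those receiving traditional education. Both fit a fixed indicator, under which a gain shared by everyone does not reach the class OR (step 4). This stands as a condition on the finding. It does not dispose of it: a fixed indicator never changes within a person, so the SAP's claim that each subject is his or her own control would have no class contrast behind it.

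Second, equation (1) writes no person intercepts, the multilevel part is described as medical institutions, and gender and race could not be estimated under person fixed effects. A reader might infer that the reported OR would carry the whole yearly gain. The documents do not support that for the mixed model, where non-takers offset part of it (step 2).

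Third, a reader might infer that the class OR must be inflated. No document says that scores rise over a year. If they fall, the bias runs against the classes.

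Fourth, finely recorded age could absorb a little of the change, and longer panels reduce the bias. Both points are fair, but neither supplies a start/end term.

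Finally, the covariates listed (intended specialty, medical school) fit track 1 only, so nothing here extends to the health-record data of the other tracks.

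**Conclusion.** The point holds conditionally. The listed covariates and equations contain no term for start versus end of year. If exposure is coded as changing between those surveys, ordinary change over the year enters the class OR: wholly in a pure within-person contrast, and partly in the mixed model. With a true class OR of 1.0 the mixed model gives about 1.2, 1.3 and 1.6 for assumed gains of 1.25, 1.5 and 2.0 in a two-survey panel with person SD 1.5, and less in longer panels with a school-year term.

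This rests on three assumptions: time-varying exposure coding, which best fits protocol section 3 and the within-person claim but is not stated; a non-zero ordinary change of unknown size and direction; and the simulated uptake and person SD.

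The SAP's objection to difference-in-difference does not rescue the design. Its own within-person contrast is open to the same time-varying influences and, without a time term, also leaves out the non-takers' change. It would go too far to say that the plan must therefore withdraw its sentence on difference-in-difference or add calendar-year terms. In the simulations a start/end indicator alone brought the OR back to about 1.

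**What to change.** 1. State how exposure is coded at each survey, including start-of-year surveys in years after a trainee has taken classes.
2. Add a start/end-of-year indicator to equation (1), optionally crossed with school year so that the ordinary change may differ between years of training.
3. Keep non-takers in the model, since they identify the ordinary change.
4. Define the class effect as the extra start-to-end change in those who took classes that year.

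The cost is SAP wording, one or a few model terms, and a slightly wider interval for the class OR. No new data are needed, because non-takers are already offered both surveys.
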